8.3.23. Pharmacokinetic Assessments

Samidorphan, RDC-9986 (primary metabolite of samidorphan), and olanzapine concentrations will be determined from plasma samples collected according to [Table 1](#), [Table 2](#), and [Table 3](#). The time of last study drug administration (when applicable) and the associated pharmacokinetic (PK) blood draw must both be recorded in a subject's source documents. Samples for PK

analysis will be stored at $-20^{\circ}\text{C} \pm 10^{\circ}\text{C}$. These PK data may be included in a subsequent population PK analysis or other post-hoc analyses conducted outside of this study.

8.3.24. Body Height, Body Weight, and Waist Circumference

Body weight (in kilograms) will be measured 3 times whenever weight is being assessed. The median weight will be entered into an electronic data capture system. The median is the middle number when the 3 measures are put in numerical order (eg, in the sequence 1, 2, 3; the median number is 2). Subjects should be asked to void immediately prior to the body weight measurement. Subjects should be weighed on the same scale for each measurement under the same conditions. Conditions should be as consistent across visits as possible. Subjects should remove all personal items, such as watches and jewelry, prior to body weight measurement. Subjects should be weighed in hospital gowns with a consistent amount of undergarments for each measurement.

At each time that body weight is measured, waist circumference (in cm) will also be measured. These measurements will be made where indicated in [Table 1](#), [Table 2](#), and [Table 3](#).

Height (in cm) will be collected at screening only (see [Table 1](#)).

8.3.25. 12-Lead Electrocardiogram

A 12-lead ECG will be recorded as specified in [Table 1](#), [Table 2](#), and [Table 3](#). All scheduled ECGs must be performed after the subject has rested quietly for at least 5 minutes in the supine position.

A qualified clinician will conduct ECGs and assess ECG results using equipment that has been calibrated according to the site's standard operating procedures. The following ECG parameters will be collected: pulse, RR, PR, QRS, QT, QTcF, and QT interval corrected using the Bazett Formula (QTcB).

ECGs will also be evaluated by a central reader.

8.3.26. Supportive Counseling

Supportive counseling will be provided as per investigator's judgment as specified in [Table 2](#), and [Table 3](#). Counseling will focus on the following:

1. Disease education
2. Encouragement of treatment adherence
3. Crisis intervention

The person who conducts supportive counseling sessions should not assist the subject with TLFB.

8.3.27. Drug Dispensation and Reconciliation

[Section 9](#) provides information related to drug dispensing procedures. Study drug will be dispensed at the time points specified in [Table 1](#), [Table 2](#), and [Table 3](#). The study drug use and storage information will be explained to and reviewed with the subject.

Whether or not samidorphan is classified as a controlled substance varies from country to country; some countries have classified samidorphan as a controlled substance, but others have not. Sites will be given handling, storage, and reconciliation instructions applicable to their country to ensure compliance with local regulations for controlled substances.

Olanzapine will be dispensed by the site.

Samidorphan/placebo and olanzapine will be provided in separate containers (eg, blister cards and bottles). Subjects will be instructed to keep all unused tablets in their original containers and not combine pills into a single container. Subjects will also be instructed to return the original containers and any remaining study drug(s) (both olanzapine and samidorphan/placebo, as applicable) at each visit following dispensation. Study drug should not be re-dispensed to the subject after the containers have been returned. Study drug accountability will be documented as the number of tablets dispensed, dosed, lost/missing, or remaining. If applicable, the site will discuss noncompliance with the subject.

8.3.28. Emergency Treatment Card

An emergency treatment card will be distributed to each subject and collected from each subject at the timepoints specified in [Table 1](#) and [Table 3](#). The card will indicate that the subject may be receiving an opioid antagonist and/or olanzapine and will include the PI's contact information, a suggested pain management plan, and information regarding opiate blockade. Subjects will be instructed to keep the emergency treatment card with them at all times. Study personnel will confirm that the subjects have the card in their possession at each study visit indicated on [Table 1](#), [Table 2](#), and [Table 3](#).

8.4. Study Requirements and Restrictions

8.4.1. Contraception and Pregnancy

All male and female subjects must agree to use an acceptable method of contraception for the duration of the study. At a minimum subjects must agree to use one of the following. Additional restrictions, if required, will be clarified in the locally-approved ICF or are clarified below.

- Double-barrier protection (eg, a condom with spermicide or a diaphragm with spermicide)
- Intrauterine device
- Oral contraceptive pills and other hormonal methods (eg, a vaginal ring, contraceptive patch, contraceptive implant); oral contraceptives must have been initiated at least 30 days prior to screening

Subjects must agree to use one of the following acceptable methods of contraception for the duration of the study:

- Condom (barrier method) plus
 - Intrauterine device
- or

- Hormonal contraceptive (such as birth control pills or patches, a vaginal ring, or a contraceptive implant); oral contraceptives must have been initiated at least 30 days prior to screening

Subjects who are abstinent are eligible to be in this study, provided they agree to use an acceptable contraceptive method should they become sexually active.

Subjects who are surgically sterile are exempt from the requirement to use contraception. Women who have undergone a hysterectomy, bilateral tubal ligation, or bilateral salpingo-oophorectomy are considered surgically sterile. Men who have undergone a vasectomy are considered surgically sterile. Partner vasectomy is not considered an approved acceptable method of contraception for a female subject.

Women who are postmenopausal are also exempt from the requirement to use contraception. For the purpose of this study, postmenopausal is defined as the permanent cessation of menstruation for at least 12 months prior to screening in women who are 45 years of age or older.

If any female subject becomes or is found to be pregnant while participating in the study, she will be discontinued from study drug immediately. The investigator must fill out a Pregnancy Report Form and submit the information to the sponsor within 24 hours of awareness of the pregnancy, irrespective of whether an adverse event has occurred. The early termination and safety follow-up visits will be scheduled.

The investigator will follow the pregnancy until completion or until pregnancy termination and notify the outcome to the sponsor. If the outcome of the pregnancy meets the criteria for immediate classification as a SAE the investigator should follow the procedure of reporting SAEs (see [Section 13.2](#)).

8.4.2. Prohibited and Restricted Medications

The following medications are prohibited or restricted during the study period (unless otherwise noted) except when subjects are tapering off of the medication as described in [Section 8](#). Trade names may be different outside of the US:

- Monoamine oxidase inhibitors (eg, phenelzine, tranylcypromine, selegiline, or moclobemide) are prohibited.
- Mood stabilizers (eg, lamotrigine, lithium, valproic acid, carbamazepine) are prohibited (except prior to Visit 8 when medically indicated)
- Long-acting formulations of any antipsychotic and any form of clozapine are prohibited during the screening and study period.
- Benzodiazepines (except prior to Visit 8 when medically indicated) are prohibited
- Antidepressants are prohibited if it is anticipated that the dose will change during the subject's participation in the study. The medical monitor should be contacted with any questions about the appropriateness of including a subject taking an antidepressant medication. Antipsychotic use for depression is prohibited

- Varenicline (Chantix[®]) is prohibited. Other nicotine replacement therapy (eg, nicotine replacement patch or oral nicotine gum) is permitted if the subject regularly used the therapy prior to screening.
- Alcohol-treatment-related medications including, but not limited to, the following: naltrexone (ReVia[®]/Depade[®]), Vivitrol[®], naloxone, acamprosate (Campral[®]) and disulfiram (Antabuse[®]) are prohibited throughout the study period.
- In general, the use of psychotropic medications other than study drug is discouraged during the study period, with the exception of the following:
 - Beta-blockers (eg, propranolol or pindolol), antihistamines, and anticholinergics may be used for treatment-emergent akathisia.
 - Anticholinergics may be used for extrapyramidal symptoms.
 - Non-benzodiazepine medication may be used to treat insomnia.
- Topiramate (Topamax[®]) and combination products containing topiramate are prohibited.
- Opioid agonists should be avoided (see Section 8.4.4 for details on pain management).
- Opioid antagonists are prohibited through the follow-up period.
- Inducers or moderate to strong inhibitors of CYP3A4 (prescription medications, over-the-counter medications, or dietary supplements) are prohibited through the follow-up period. See [Appendix L](#) for a partial list of prohibited CYP3A4 inducers and moderate to strong inhibitors.
- Medications that are contraindicated with olanzapine use or exhibit drug-interaction potential with olanzapine will be defined and prohibited at the discretion of the PI.

8.4.3. Other Prohibited Substances

Prohibited substances during the study period include amphetamines (including methamphetamine), cocaine, barbiturates, methadone, opiates (including morphine, oxycodone, methadone, and buprenorphine), and phencyclidine. Screening procedures for these substances are described in [Section 8.3.5](#). Except as noted in Section 8.3.5, the PI will exercise his/her medical judgment as to whether or not subjects using any prohibited substances should be deemed ineligible or withdrawn.

Tobacco and/or caffeine use is allowed if the daily amount used is anticipated to remain relatively stable throughout the study period.

8.4.4. Pain Management

Because ALKS 3831 contains samidorphan, a μ -opioid receptor antagonist, subjects may experience reduced or ineffective analgesia when taking an opioid analgesic agent concurrently with ALKS 3831, including several days after last dosing of ALKS 3831.

In the event of an emergency, pain management of the subject should include the following:

- Regional analgesia or use of non-opioid analgesics
- If opiate anesthesia or analgesia is required, the subject should be continuously monitored in an anesthesia care setting by persons not involved in the conduct of the surgical or diagnostic procedure. The opioid therapy must be provided by individuals specifically trained in the use of anesthetic drugs and the management of the respiratory effects of potent opioids, specifically the establishment and the maintenance of a patent airway and assisted ventilation.
- Close monitoring by appropriately trained personnel in a setting equipped and staffed for cardiopulmonary resuscitation

For subjects requiring emergency opioid analgesics prior to dosing, the study drug should not be administered. If opioid analgesics are required after the study drug has been dosed, it may take several days for opiate sensitivity to be restored, since samidorphan is an opioid antagonist and could interfere with opioid-mediated pain management.

8.4.5. Rescue Medication

The PI is responsible for all trial-related medical decisions for subjects enrolled at his/her site and can always administer rescue medication without consulting the medical monitor.

Administering rescue medication is considered an EEDS for this trial (see [Section 11.1](#)). The PI or designee should document the reason(s) for the rescue medication and the designated treatment(s). Examples of rescue medication include (but are not limited to):

- An increase in olanzapine dose
- Use of a prohibited medication, such as an antipsychotic or other psychotropic medication (see [Section 8.4.2](#)), for psychiatric treatment

8.5. Ad Hoc Study Visits

When a subject meets a criterion for an EEDS that requires a second assessment (see [Section 11.1](#)), an ad hoc study visit should be scheduled for 3 days after the first assessment when it is possible and does not compromise subject safety. Otherwise, the ad hoc visit should be scheduled within 7 days of the first assessment.

If, despite all reasonable efforts by the site, a second assessment cannot be completed within 7 days, the event will be considered an EEDS.

Assessments completed at the ad hoc study visit should include AE monitoring, concomitant medication review, C-SSRS (“Since Last Visit”), CGI-S, CGI-I, PANSS, and EEDS criteria review. Any assessment that needs to be confirmed from the first assessment should be completed before any other assessments.

9. TREATMENT OF SUBJECTS

9.1. Study Drug Dose and Administration

Study drugs include samidorphan and matching placebo tablets, and olanzapine tablets, all for oral administration.

For all subjects, open-label samidorphan 10 mg will be taken once daily for 2 weeks prior to randomization. For subjects in the double-blind treatment period, samidorphan 10 mg (or placebo) will be taken once daily for up to 15 months.

For all subjects, the dose of olanzapine will be taken once daily (to be taken at the same time as samidorphan/placebo) at an individualized dose level. Olanzapine initiation, including transition from another antipsychotic (as applicable), is a highly individualized process. Formalizing the potential clinical scenarios may pose undue burden and/or risk to subjects. Clinical judgment is essential, and for this reason, the details of this process are left to the discretion of the treating physician, who will follow current clinical practice.

All subjects will be administered olanzapine for 11 to 17 months as part of this clinical trial.

ALKS 3831 should be taken as close to bedtime as possible. Subjects should not drive or operate heavy machinery until they know how ALKS 3831 will affect them.

After Visit 5, the dose level of olanzapine will be fixed, and an increase in dose level above the dose set at Visit 5 prior to randomization may cause the subject to be discontinued. The olanzapine dose level may be decreased at any time if the PI considers it medically beneficial to the subject, such as when a subject has stable psychiatric symptoms with side effects that may be reduced if the olanzapine dose level is decreased. If the PI decreases the dose level after randomization, only an increase above the dose level at randomization will be considered an EEDS.

At study drug dispensation visits, all subjects will receive blister cards containing samidorphan or placebo for self-administration; subjects will also receive olanzapine in separate packaging. Subjects will be instructed to take 1 tablet per day from the blister card in addition to their olanzapine tablet(s) once daily in the evening or at bedtime. The subject will take the final samidorphan/placebo dose the night before the final visit of the double-blind treatment period. Olanzapine dosing will continue uninterrupted through the end of the study. Any subject who prematurely discontinues from the study will be asked to return to the clinic for an ET visit and 2 safety follow-up visits.

9.2. Treatment Adherence

Subjects who, in the opinion of the PI or designee, have demonstrated treatment adherence during the open-label olanzapine and ALKS 3831 treatment period will be randomized to double-blind treatment (samidorphan or placebo). Study personnel may be able to identify non-adherence during study visits (eg, based on responses during clinical assessments) and may also ask the subject or caregiver (if applicable) directly about adherence. Additional measures of adherence may be used at the sponsor's and PI's discretion. During the double-blind treatment

period, supportive counseling sessions will be used to encourage treatment adherence. Study staff will address non-adherence with the subject as needed.

9.3. Randomization to Treatment

At Visit 8, subjects will be randomized to receive one of the following regimens in a 1:1 ratio:

- Olanzapine + Samidorphan (10 mg)
- Olanzapine + Placebo

Randomization will be performed centrally through an Interactive Web Response System (IWRS). A unique randomization number will be assigned by an IWRS once eligibility has been determined. Once a randomization number has been assigned, that number must not be used again if, for example, a subject is withdrawn from the study. Codes will be prepared by a third-party biostatistician who is not otherwise involved in this study.

9.4. Blinding

All Alkermes staff, clinical staff, subjects, and caregivers will remain blinded to treatment assignment until the final database lock. All PPD staff will remain blinded except when their study function requires unblinding (eg, drug supply management, IWRS operation, etc). These unblinded staff will follow standard operating procedures to ensure that they do not bias the study.

The PI is responsible for all trial-related medical decisions. Emergency unblinding may be done without contacting a medical monitor. Any premature unblinding should be promptly documented and explained to the medical monitor within 24 hours following disclosure of study drug assignment.

If the PI is unsure whether unblinding is needed, he or she may contact the PPD or Alkermes medical monitor before the blind is broken.

Breaking the blind for a single subject will not affect the blind for the remaining subjects.

10. STUDY DRUG MATERIALS AND MANAGEMENT

10.1. Study Drug

Commercially available olanzapine will be supplied by the investigative site.

Samidorphan will be provided by Alkermes in 10 mg tablets.

Placebo consists of tablets, identical in size and appearance to the samidorphan tablets.

Subjects will take 1 tablet per day orally (either samidorphan or placebo) at the same time as their olanzapine.

10.2. Packaging and Labeling

Samidorphan and placebo will be packaged in blister packs. Blister cards will be provided in biweekly configurations. The biweekly blister card will contain 16 tablets, which provides 2 weeks of dosing with sufficient overage to allow for 2 additional daily doses.

Blister card labels will meet all applicable local and regulatory requirements.

10.3. Storage

Whether or not samidorphan is classified as a controlled substance varies from country to country; some countries have classified samidorphan as a controlled substance, but others have not. Sites will be given storage instructions applicable to their country to ensure compliance with local regulations for controlled substances.

10.4. Accountability

The clinical site is required to maintain current drug dispensation and accountability logs throughout the study. All unused supplies will be checked against the drug movement records during the study and/or at the end of the study.

Refer to [Section 8.3.27](#) for additional study drug reconciliation procedures.

10.5. Handling and Disposal

Following completion and verification of accountability logs, all unused and used packages must be destroyed. Alkermes may arrange for destruction with a third party agent operating in accordance with GCP.

11. ASSESSMENT OF EFFICACY

11.1. Primary Efficacy Measure

The primary efficacy measure is an EEDS, defined as any of the following occurring during the double-blind period and is related to worsening of disease symptoms, as confirmed by the IAC:

1. Subject requires hospitalization due to worsening of disease symptoms including a psychiatric hospitalization or a hospitalization due to or for acute treatment of alcohol intoxication or withdrawal
2. Subject has a $\geq 25\%$ or ≥ 15 -point increase from randomization in PANSS total score that is confirmed at a second, ad hoc visit shortly after the first assessment (see [Section 8.5](#))
3. Subject has a PANSS item score of P1, P2, P3, P6, P7, or G8 that meets one of the following criteria:
 - For subjects with a score ≤ 3 at randomization, a score ≥ 5 that is confirmed at a second, ad hoc visit shortly after the first assessment (see [Section 8.5](#))
 - For subjects with a score of 4 at randomization, a score ≥ 6 that is confirmed at a second, ad hoc visit shortly after the first assessment (see [Section 8.5](#))
4. Subject commits deliberate self-injury, engages in aggressive behavior, or displays signs of suicidal or homicidal ideation that is clinically significant as judged by the PI
5. Subject requires initiation of rescue medication (see [Section 8.4.5](#)), including an increase in prescribed olanzapine dose level, due to worsening of disease symptoms
 - For this study, the increase in olanzapine dose must be above the randomization dose level even if the dose level was previously decreased at some point after randomization.
6. Subject requires an emergency room visit due to worsening of disease symptoms
7. Subject withdraws or PI discontinues the subject from the study for one of the following reasons:
 - a. Lack of efficacy
 - b. Lost to follow-up
 - c. Withdrawal by subject
8. Subject is involved in an incident leading to arrest or incarceration during the study period that is related to the subject's underlying disease

For criterion requiring a consecutive assessment, the second assessment should be scheduled within 3-7 days of the first occurrence and conducted as per [Section 8.5](#). All EEDS cases will be reviewed by the IAC in a blinded manner. Only events confirmed by the IAC will be used for efficacy analyses. Further details on the functioning of the IAC will be included in the IAC charter.

If no withdrawal criteria have been met, subjects experiencing an EEDS (except event #7) may continue in the study at the discretion of the PI.

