7.4. Subject Withdrawal

A completer is defined as any subject who completes the double-blind treatment period. A subject may be discontinued from the study at any time if the subject, PI, or Alkermes determines that it is not in the best interest of the subject to continue participation. Reasons for discontinuation include the following:

- AE
 - Note: An absolute neutrophil count $\leq 1.0 \times 10^3$ per μL anytime while on olanzapine should be cause for discontinuing a subject.
- Lack of efficacy
- Lost to follow-up
- Protocol violation (non-compliance with study drug or study procedures)
- Withdrawal by subject (eg, withdrawn consent)
- Pregnancy
- Study terminated by sponsor
- Other

If a subject withdraws from the study at any time for any reason, any ongoing AEs will be followed until resolution, until deemed stable by the PI, or until the subject is deemed by the investigator to be lost to follow-up. If, in the opinion of the PI or designee, it is necessary to monitor a subject beyond the safety follow-up visit, the follow-up period may be extended as necessary. In such instances, Alkermes and the PI will agree to an acceptable follow-up schedule.

In the event that a subject chooses to withdraw from the study, the PI should make a reasonable effort to ascertain the reason(s) for withdrawal, while fully respecting the subject's rights. The subject should be encouraged to return to the study center for an early termination (ET) visit, which will match the procedures at Visit 38 (see [Section 8](#)), and to complete a subsequent safety follow-up period. The safety follow-up period for subjects who discontinue early should mirror the safety follow-up visits displayed in [Table 3](#). If the subject fails or refuses to return to the study center, an attempt must be made to contact the subject by telephone in order to assess as many safety and efficacy parameters as possible. All data collected over the telephone must be documented and kept in the subject's record.

The investigator must maintain a record of all subjects who fail to complete the study. A full explanation of the reason for study discontinuation will be made on the appropriate electronic case report form (eCRF).

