13.1. Definition of Adverse Event

An AE is any untoward medical occurrence in a patient or clinical investigation subject administered a pharmaceutical product. The occurrence, which may or may not have a causal relationship with the investigational treatment, may include any clinical or laboratory change that does not commonly occur in that subject and is considered clinically significant.

Illnesses present prior to the subject signing the ICF are considered to be pre-existing conditions and are documented on the medical history eCRF. Pre-existing conditions that worsen during the study are entered on the AE eCRF.

All out-of-range laboratory values will be deemed as clinically significant or not clinically significant by the investigator. Clinically significant values will be considered AEs and recorded as such on the eCRFs.

Pregnancy is not considered an AE, although a subject will be withdrawn from the study if a pregnancy occurs. As described in [Section 8.4.1](#), the pregnancy must be reported to Alkermes and additional follow-up may be required.

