14. STATISTICS

14.1. Sample Size Considerations

The sample size calculation is based on the detection of log-hazard ratio for the first EEDS during the double-blind treatment period.

Based on the previous clinical studies with olanzapine and clinical judgment, the 9-month cumulative proportion of subjects experiencing an EEDS will be 15% and 30% for the ALKS 3831 group and olanzapine plus placebo group, respectively. Assuming an exponential distribution of survival time, and a 2-sided test at $\alpha=0.05$, a total of 70 EEDS will be required for approximately 90% power to detect a hazard ratio of 0.45 between ALKS 3831 and olanzapine plus placebo with a randomization allocation ratio of 1:1 (ALKS 3831:olanzapine plus placebo). Approximately 270 subjects (135 subjects per treatment group) will need to be randomized at Visit 8 to observe 70 total EEDS.

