Subjects who completed or discontinued the double-blind period without an EEDS will be censored at the last EEDS assessment date. For all other subjects with EEDS, the date of first EEDS will be counted as event date.

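### A discontinuation for worsening disease that meets no other EEDS criterion can become a primary event if recorded as lack of efficacy, but is censored if recorded as an AE

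*Protocol*

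**What the plan says.** Criterion 7 is worded identically in Protocol 11.1 and SAP 3.7.2: "Subject withdraws or PI discontinues the subject from the study for one of the following reasons", followed by (a) lack of efficacy, (b) lost to follow-up and (c) withdrawal by subject. As with every EEDS, the IAC must confirm that the event is related to worsening of disease symptoms.

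Three other places bear on this:

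- Protocol 7.4 gives the site its list ("Reasons for discontinuation include the following"). AE comes first and lack of efficacy second. Nothing says how to choose when both fit.
- Protocol 13.1: "Pre-existing conditions that worsen during the study are entered on the AE eCRF". Schizophrenia and AUD are pre-existing conditions for every subject in this trial.
- SAP 3.7.2: "Subjects who completed or discontinued the double-blind period without an EEDS will be censored at the last EEDS assessment date".

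SAP 3.7.2.2 has two sensitivity analyses. The first censors events that rest only on 7b or 7c, or for which the IAC names no criterion. The second turns a random 10%, 20% or 30% of event-free discontinuers into events, whatever their reason for leaving.

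**The concern.** The same clinical exit can take two routes through the endpoint. If the investigator stops a subject because psychosis or drinking is getting worse and records lack of efficacy, the IAC sees a case. If the investigator records AE, criterion 7 is not met. On the wording of Protocol 11.1 there is then no EEDS case to review, unless some other criterion applies. Blinded adjudication can reject a case that was wrongly referred, but it cannot recover one that was never referred.

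The log-rank test and the Cox model treat that censoring as uninformative, although the subject left because of the disease the endpoint is meant to capture. Subjects who withdrew or were lost to follow-up, about whom less is known, do have a route to the IAC through 7b and 7c. What is at stake is some loss of events and, if coding habits differed between arms, a distorted hazard ratio.

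**Working it through.** **Following one subject through the plan.** Take a subject discontinued for worsening who has met none of criteria 1 to 6 or 8.

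| Step | Recorded as lack of efficacy | Recorded as AE |
|---|---|---|
| Allowed by Protocol 7.4 | Yes | Yes |
| On criterion 7's list | Yes (7a) | No |
| EEDS case for the IAC on the text of Protocol 11.1 | Yes | No |
| Primary analysis | Event if the IAC confirms, otherwise censored | Censored at last EEDS assessment |
| First sensitivity analysis, SAP 3.7.2.2 | A confirmed 7a event stays an event | Stays censored |
| Second sensitivity analysis, SAP 3.7.2.2 | A confirmed event is unaffected | Becomes an event only by random draw |

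**Who is left in that group.** Criteria 1 to 6 and 8 cover hospitalization, confirmed PANSS worsening, self-injury, aggression or ideation, rescue medication, emergency room visit and arrest. They apply whatever discontinuation reason is recorded. Protocol 8.5 also counts a PANSS threshold rise whose second assessment could not be done within 7 days. The early termination visit includes PANSS and an EEDS criteria review (Protocol 7.4 and Table 3). What remains is mainly sub-threshold psychotic worsening, and worsening drinking that led to none of these. Drinking by TLFB is a separate efficacy measure, not an EEDS criterion.

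**The plan's own figure.** Protocol 14.1: "a total of 70 EEDS will be required for approximately 90% power to detect a hazard ratio of 0.45", 2-sided 5% level, 1:1 allocation.

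- Schoenfeld events: D = 4 × (1.960 + 1.282)² / (ln HR)².
- At HR 0.45, D = 66. At the HR implied by 15% and 30% at 9 months, ln 0.85 / ln 0.70 = 0.456, D = 69. The stated 70 is consistent with this.
- Power = Φ(√(D/4) × |ln HR| − 1.96). At 70 events it is 91.6% for HR 0.45 and 90.8% for HR 0.456.

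**Equal loss in both arms.** The documents give no rate. Assume that 2% to 6% of the 270 randomized subjects fall in the group and that all would have been confirmed: 0.02 × 270 ≈ 5 and 0.06 × 270 ≈ 16, or 7% to 23% of 70 events. With HR 0.45 and |ln 0.45| = 0.7985:

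| Events D | √(D/4) × 0.7985 − 1.96 | Power |
|---|---|---|
| 70 | 1.38 | 92% |
| 65 | 1.26 | 90% |
| 60 | 1.13 | 87% |
| 54 | 0.97 | 83% |

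Expressed instead as losing 5%, 10%, 20% or 30% of the 70 events, power at HR 0.456 is 89.3%, 87.7%, 83.7% or 78.6%.

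**Unequal loss.** If a fraction f_T of ALKS 3831 events and f_C of control events is censored, the apparent HR is roughly HR × (1 − f_T)/(1 − f_C). From 0.456:

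- 10% or 20% of ALKS 3831 events only: 0.410 or 0.365.
- 10% or 20% of control events only: 0.506 or 0.570. Power is 82.9% or 64.6%, taking follow-up as uniform over 9 to 15 months with no dropout.
- With a true HR of 1, 10% or 20% of ALKS 3831 events only: 0.90 or 0.80.

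These are what-if values. Nothing in the documents indicates that coding would differ by arm.

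**The case against.** The strongest reply is that the residual group is narrow. The subject must be ill enough to be stopped, yet have triggered none of seven other criteria, the Protocol 8.5 rule, or the review at the early termination visit. Protocol 11.1 also lets subjects stay in the study after most EEDS, so worsening need not end participation. This stands, and it is why the point is a modest one. It does not empty the group: attendance at the early termination visit is encouraged rather than assured, and criterion 7a would be redundant if the other criteria caught everything.

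A reader might infer that the recorded reason alone settles the endpoint. The documents do not support that. Lack of efficacy counts only if the IAC confirms relatedness, and AE leads to censoring only when nothing else qualifies. Nor does Protocol 13.1 oblige the site to give AE as the discontinuation reason; it only requires the worsening to be entered as an AE. A reader might also infer that every such exit is a lost true exacerbation. Many would be below the protocol's own thresholds, and the IAC might not confirm them.

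Other replies stand in part:

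- The IAC charter is cited but is not among the documents. It may already route these cases, and SAP 3.7.2.2 allows for a confirmed event with no named criterion.
- The second sensitivity analysis does cover AE exits, but at random, regardless of reason and with no contrast between arms.
- AEs leading to discontinuation (SAP 3.8.1) and time to study drug discontinuation (SAP 3.7.5) are reported by arm. Uneven coding might show there, but it would not be adjudicated.
- With follow-up uniform over 9 to 15 months and no dropout, about 77 events are expected, so a loss of 5 still leaves 72. A loss of 16 leaves 61.

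**Conclusion.** The gap is real but narrow. For a subject discontinued for worsening schizophrenia or AUD whose worsening reaches the endpoint only through criterion 7, the site's choice between two permitted labels decides whether the IAC has a case or the subject is censored. Neither planned sensitivity analysis isolates these subjects.

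The effect on power is probably modest: from about 92% to between 90% and 83% at HR 0.45. That rests on an assumed loss of 5 to 16 of 70 events, equal in both arms, with every case confirmable. The loss rate is not in the documents. It is tempting to go further and call the hazard ratio biased. The documents give no ground for expecting different coding by arm, so bias remains a risk to guard against. The plan's sample-size figures reproduce and are not in question. If the charter already sends these exits to the IAC, the defect reduces to the protocol and SAP not saying so.

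**What to change.** 1. In SAP 3.7.2, and in Protocol 11.1 and the IAC charter if they can still be amended, state that a discontinuation recorded as AE is referred to the blinded IAC when the AE is a worsening of schizophrenia or AUD, under the same relatedness standard as 7a. Identify these cases blind to treatment, from a pre-specified list of psychiatric and alcohol-related preferred terms.
2. In SAP 3.7.2.2, add a sensitivity analysis of the primary endpoint that counts the IAC-confirmed cases as EEDS on the discontinuation date. Have the IAC record them under their own label, so that the existing rule on events without a named criterion does not censor them.
3. If the charter already routes these cases, say so in the protocol and SAP.

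Adding AE as a new item under criterion 7 would go further, but it redefines the primary endpoint and is more debatable. Keeping AE exits out of criterion 7 can be defended as separating tolerability from efficacy failure. The steps above leave the primary definition as it is.

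The cost is a few more adjudications, a term list fixed before unblinding, and one more analysis. AE terms and discontinuation reasons are already collected, and Protocol 7.4 requires a full explanation of the reason on the eCRF. Only endpoint classification changes, not how subjects are managed.
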